Purpose of the clinical investigation / Objectif de l'investigation clinique	
The Epione device is a robotic device that assists the physician during CT-guided percutaneous treatment. This device is validated in clinical practice for abdomen and lung. The state of the art in percutaneous bone procedures and the observation of current practices highlighted the need to explore the use of the Epione device in this new indication.
 
The aim of this clinical investigation is to confirm in patients the performance and safety of the Epione device designed to assist radiologists during percutaneous procedures in musculo-skeletal structures in view of the satisfactory results obtained during preclinical tests.

Primary objective and endpoint / Objectif et critère d'évaluation primaire	
Primary objective: Evaluate the feasibility of the Epione robotic assistance for bone percutaneous procedures.
 
Primary endpoint: successful instrument insertion with the Epione device

Secondary objectives and endpoints / Objectifs et critères d'évaluation secondaires	
Secondary objectives:
 
 • Evaluate the safety of the Epione robotic assistance for bone percutaneous procedures • Evaluate the accuracy of the Epione robotic assistance for bone percutaneous procedures 
Secondary criteria:

Investigation Number: EPIBONE

ClinicalTrials.gov ID:

CIV-ID: 2024-A00468-39

Document title: EPIBONE Clinical Investigation Synopsis

Doc No: CA-BO-SYN-0053

Revision: B

	
• Adverse event(s) (AE): all AEs (serious and non-serious, related and not-related to the device or the procedure(s))• Lateral and angular deviations:
◦ distance (mm) between the tip of the inserted instrument in its final position and its orthogonal projection on the first planned trajectory.◦ and angle (°) between the tip of the inserted instrument in its final position and the first planned trajectory. (the special case of using a rod through the introducer is described in the protocol)
Eligibility criteria / Critères d'éligibilité	
Inclusion criteria
 
• Patient ≥ 18 years,• Patient approved for CT-guided percutaneous bone procedure under general anaesthesia at a multidisciplinary consultation meeting,• Patient who has signed an informed consent form,• Patient covered by a social security system• Patient who has already been included in the EPIBONE study for one or more given musculoskeletal disorders and for whom a new location is targeted for a CT-guided procedure that can be assisted again by the EPIONE device. 
Exclusion criteria
 
• Patient unable to undergo general anaesthesia,• Patient offered a procedure without appropriate breathing control,• Patient approved for CT-guided percutaneous procedures on head and neck, including skull and cervical vertebrae• Patient unable to fully understand all relevant aspects of the clinical study necessary for his/her decision to participate, or who could be manipulated or unduly influenced as a result of a compromised position, expectation of benefits or fear of retaliatory response• Pregnant or breast-feeding women,• Patient subject to a legal protection measure,• Patient already participating in another interventional clinical study,
Device and comparator / Dispositif et comparateur	
The Epione investigational device is a user controlled, stereotactic accessory intended to assist in the planning and manual advancement of one or more instruments, as well as in verification of instrument position during Computed Tomography (CT) guided percutaneous procedures.
 
The device is indicated for use with rigid straight instruments such as needles and probes used in CT-guided interventional procedures performed by physicians trained for CT procedures on musculoskeletal structures.
 
The Epione device is composed of 3 main components (Robot cart, Display cart with software and Navigation cart) and 3 instruments (Introducer guide, Patient reference and Navigation probe).
 
During the planning phase, the desired instrument placement and performance is defined relative to the target anatomy.
 
During the guidance phase, the device enables to monitor respiratory levels and verify patient position prior to instrument advancement.
 
During the assessment phase, the achieved instrument placement and performance are displayed relative to the previously defined plan through an overlay of the pre- and post-treatment image data.

Investigation Number: EPIBONE
 ClinicalTrials.gov ID:
 CIV-ID: 2024-A00468-39

Document title: EPIBONE Clinical Investigation Synopsis

Doc No: CA-BO-SYN-0053
 Revision: B

	
There is no comparator.

Procedures to use the device / Procédure d'utilisation du dispositif	
The Epione device must be used in accordance with the instructions given in the study investigator brochure (CA-BO-IBR-0068). The device is a medical device reusable, non-sterile intended to be mobile. The 3 instruments of the system (guide to introduce, patient reference and navigation probe) are reusable and must be cleaned and sterilized after each use. The user of the device is a Doctor specialized and trained in CT-guided interventional procedures.
 
Procedures that can be carried out using the instrument inserted into the human body with Epione's assistance include thermal ablations, biopsies and bone consolidation procedures (osteoplasties and/or osteosyntheses), either alone or in combination.

Study flowchart / Organigramme de l'étude	
The diagram illustrates the study timeline. It starts with a 'Pre-intervention consultation' leading to 'Visit 0' (V0=D0). This is followed by an 'Inclusion visit' and the 'Day of the intervention'. After 'Visit 0', the timeline continues to 'Visit 1' (D0+3w ≤ V1 ≤ D0+8w), which includes a 'Follow-up visit' and a 'Post-intervention visit'.

	
The interventional radiologist will explain to the patient the planned procedure(s) and will present the response plan and its different steps during a pre-intervention consultation. The investigator:
 
 - will present the study and the device to the patient (oral and written information), - will review the inclusion and non-inclusion criteria of the study, and assess the patient's eligibility for the study, - Will provide the information letter and informed consent form to the patient, who must be able to read them and have time to think about his or her potential participation in the study prior to consent. - 
Demographics/medical data prior the intervention will be collected the day of the intervention if the patient returns a signed consent form and the investigator confirms the eligibility criteria. No data will be collected while prior intervention consultation, before signature of the written consentment.

Sample size / Taille de l'échantillon	
The size of the sample of at least 67 insertions was calculated to assess the non-inferiority of the successful insertion rate of the introducer (with the help of EPIONE), using a reference proportion of 96% and with a non-inferiority threshold of 0.08 under the assumption of 97% of feasibility for the study.
 
In line with centers practice, that is to say an average of 2 insertions per patient (different locations of possible musculoskeletal disorders, different possible treatments during the same procedure), it is planned to include a minimum of 34 patients in this study.

Randomisation and blinding / Randomisation et aveugle	
Not applicable.

Investigation Number: EPIBONE

ClinicalTrials.gov ID:

CIV-ID: 2024-A00468-39

Document title: EPIBONE Clinical Investigation Synopsis

Doc No: CA-BO-SYN-0053

Revision: B

Statistical methods / Méthode statistiques	
analysis d'analyses
 
The statistical analysis will be performed at risk 0.05 and a power of 80%. The outcome of the primary endpoint will be assessed by a non-inferiority test compared to the results of the preclinical study.
 
The primary endpoint analysis will be performed on the mITT population (modified Intention to Treat population). The security analysis will be carried out on the security population.
 
A statistical analysis plan will be drafted and validated before the database is locked. Quantitative variables will be described using frequencies of missing and non-missing data, means, standard deviations, medians, quartiles, minimums and maximums. Qualitative variables will be described using the frequency of non-missing and of shortages, frequency and percentage by modality

Study duration per patient / Durée de l'étude par patient	
The average duration of a patient's participation in the study is 1 month. The patient's participation will be of a minimum of 3 weeks or a maximum of 8 weeks.

Study schedule / Agenda de l'étude	
Inclusion start time: Beginning of Q3 2024 Inclusion period: 6 months End of study visit of the last patient: end of Q1 2025/ Beginning of Q2 2025.

ANSM	Agence nationale de sécurité du médicament et des produits de santé / National Agency for the Safety of Medicines and Health Products
BMI	Body Mass Index
CIP	Clinical Investigation Plan
CRF	Case Report Form
DD	Device Deficiency
FU	Follow-up
ICH	International Council for Harmonization
ITT	Modified Intent To Treat
MSK	Musculoskeletal
PP	Per Protocol
SADE	Serious adverse device effect
SAE	Serious adverse event
SAP	Statistical Analysis Plan
SAS®	Statistical Analysis System®

1 - Introduction

The Statistical Analysis Plan (SAP) outlines the statistical methodology to be used for analyzing the study data and specifies the requirements for statistical programming, including tables, figures, and listings. It describes exploratory variables, populations, planned data transformations and manipulations, and other analysis details not provided in the study protocol.

The analyses described are based on the clinical study protocol revision C dated 08-Oct-2024 (ID: CA-BO-CIP-0060) and will be prepared in accordance with the International Council for Harmonisation (ICH) E9 guideline.

Statistical analyses will be conducted by the ICUREsearch biostatistics unit in collaboration with the Sponsor.

The SAP will be validated and signed off before the clinical study database lock.

2 - Objectives

2.1 Primary objective

PRIMARY OBJECTIVE	PRIMARY ENDPOINT
To evaluate the feasibility of the EPIONE robotic system assistance for bone percutaneous procedures.	Successful introducer insertion with the assistance of the EPIONE device

2.1.1 Definition of the primary endpoint

The primary endpoint is the successful introducer insertion with the assistance of the EPIONE device. Any insertion of an introducer with the EPIONE device is considered successful if it has not been converted to manual insertion.

2.2 Secondary objectives

SECONDARY OBJECTIVES	SECONDARY CRITERIA
1. To evaluate the safety of the EPIONE robotic system assistance for bone percutaneous procedures	Adverse event(s): All AEs, serious and non-serious, related and not related to the device and/or the procedure(s).
2. To evaluate the accuracy of the EPIONE robotic system assistance for bone percutaneous procedures	Lateral and angular deviations

2.2.1 Definition of secondary criteria

1- Secondary endpoint 1:

Number and description of AEs including their severity, their imputability to the device and/or the procedure(s).

2- Secondary endpoint 2:

Measure of lateral and angular deviations defined as:

- Lateral deviation (d): The distance (mm) between the tip of the inserted introducer in its final position and its orthogonal projection on the first planned trajectory.

- Angular deviation (°): The 3D angle (°) between the inserted introducer in its final position and the first planned trajectory.

2.3 Hypotheses

It is assumed that the rate of procedures successfully assisted by the EPIONE device ("feasibility") is not inferior to that observed in the preclinical study (96.4%). More specifically, a rate of 97% successful insertions has been considered in the sample size calculation.

3 - Methodology of the study

This French multicentric study is an interventional ([category 1¹](#)), pivotal, prospective, non-randomized, non-comparative, single arm study. It is being conducted on a new version of the EPIONE device without CE marking, with a view to extending its indication to CT-guided percutaneous bone procedures on MSK structures.

The patients are expected to be followed for a duration of one month (at least 3 weeks and at most 8 weeks).

The study flow chart is detailed in Appendix 1 (see Section 9.1).

3.1 Study design

3.1.1 Inclusion criteria

1. Patient ≥ 18 years,
2. Patient with indication of CT-guided percutaneous bone procedure under general anesthesia validated at a multidisciplinary consultation meeting,
3. Patient who has signed an informed consent form,
4. Patient covered by a social security system.

3.1.2 Non-inclusion criteria

1. Patient with contraindication to general anaesthesia,
2. Patient undergoing a procedure without appropriate breathing control,
3. Patient scheduled for CT-guided percutaneous procedures on head and neck, including skull and cervical vertebrae,
4. Patient with medical, psychosocial, or emotional conditions unable to fully understand the study protocol, give an uninfluenced informed consent, or meet the study requirements during its whole duration.
5. Pregnant or breast-feeding women,
6. Patient under legal protection (tutorship, guardianship, ...),
7. Patient already participating in another interventional clinical study.

3.2 Population

The study population consists of individuals who benefited from the assistance of the EPIONE robot during CT-guided percutaneous bone procedures, namely patients with musculoskeletal disorders.

¹ <https://ansm.sante.fr/uploads/2022/02/04/20220204-modalites-pratiques.pdf>

3.2.1 Sample size

The sample size calculation was performed based on a one-sample non-inferiority test design. The preclinical study showed that 96% of insertions assisted with the EPIONE device were successful. Assuming 97% feasibility with EPIONE system, with a clinically acceptable margin of 0.08, the sample size necessary to achieve 90% power and maintain the type I error rate at 5% for this non-inferiority margin was calculated to be approximately 67 insertions.

[figure not shown]
The sample size was calculated using the Cohen's arcsine transformation, which is a preferred method when dealing with proportions close to the boundaries (0 or 1) as it helps to stabilize the variance and normalize the data.

Considering the practice of the centers, i.e. an average of 2 introducer insertions per patient (different locations of MSK disorders possible, different treatments possible during the same procedure), it is planned to include a minimum of 34 patients in the study.

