5.2 Statistical tests

All tests other than the non-inferiority test of the primary endpoint will be two-sided with a global alpha risk level of 5%. A p-value less than 0.05 will be considered statistically significant. All confidence intervals will be two-sided and presented with a 95% confidence level.

The non-inferiority test of the primary criterion will be one-sided with a global alpha risk level of 5%. A p-value less than 0.05 will be considered statistically significant. Confidence interval will be one-sided and presented with a 95% confidence level.

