6.1.1 Main analysis

The objective of this study is to evaluate the feasibility of the EPIONE robotic assistance for bone percutaneous procedures. The primary endpoint of this study is the successful insertion of the introducer with the assistance of the EPIONE device. Non-inferiority of the success rate of the EPIONE device, compared to the pre-clinical study (feasibility observed during pre-clinical tests), will be concluded if the lower bound of the one-sided 95% confidence interval for the observed proportion of successful EPIONE device uses is greater than or equal to 0.88 (0.96 minus a non-inferiority margin of 0.08).

A non-inferiority test for proportions will be conducted. The variable of interest is the success rate (proportion) of the introducer insertion with the assistance of the EPIONE device. The non-inferiority test will compare the success rate observed in the study with the reference value of 0.88.

The success rate will first be calculated, followed by the computation of a one-sided 95% confidence interval for this proportion. Non-inferiority will be concluded if the lower bound of the 95% confidence interval for the success rate is greater than or equal to 0.88.

Null hypothesis (H0): The success rate is less than 0.88.

Alternative hypothesis (H1): The success rate is greater than or equal to 0.88 (non-inferiority).

The frequency and percentage of successful introducer insertions with EPIONE device assistance will be reported.

This analysis will be conducted on the mITT population.

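### At 67 insertions no cut-off gives both the 90% power and the 5% type I error stated in the SAP, and the unnamed interval method decides whether 63/67 passes

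*SAP*

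**What the plan says.** SAP 3.2.1 takes a preclinical success rate of 96%, a margin of 0.08 and an assumed true rate of 97%, and gives about 67 insertions as "the sample size necessary to achieve 90% power and maintain the type I error rate at 5% for this non-inferiority margin". It states the method: "The sample size was calculated using the Cohen's arcsine transformation". At an average of 2 insertions per patient, this becomes a minimum of 34 patients.

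SAP 6.1.1 sets the decision rule: "Non-inferiority will be concluded if the lower bound of the 95% confidence interval for the success rate is greater than or equal to 0.88". SAP 5.2 adds the level and the side: "Confidence interval will be one-sided and presented with a 95% confidence level". SAP 6.1.1 also announces a non-inferiority test for proportions. Neither section says which interval or which test. The arcsine transformation is mentioned only for the sample size.

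In the protocol synopsis, the Sample size row treats the number as a minimum ("The size of the sample of at least 67 insertions"). The Statistical methods row gives a different power: "The statistical analysis will be performed at risk 0.05 and a power of 80" percent, against 90% in the SAP.

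**The concern.** With a success rate near 97% and fewer than 70 insertions, the rule comes down to a whole number of allowed failures. A smooth approximation can promise 90% power at 5% error for a sample size at which no whole-number cut-off delivers both. The common one-sided 95% bounds also differ by more than 0.02 here, enough to move the cut-off by one failure.

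SAP section 3 describes the study as pivotal, with a view to extending the device's indication. It is a single-arm study without blinding, so failure counts are visible as they accrue. If the signed SAP leaves the interval open, the primary conclusion could depend on a method chosen once the count is known. Because 67 insertions and 34 patients are minimums, the final denominator does not fix the cut-off either.

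**Working it through.** **Inputs.** Null rate 0.96 − 0.08 = 0.88 (SAP 6.1.1). Assumed true rate 0.97, power 90%, type I error 5% (SAP 3.2.1). One-sided test (SAP 5.2). n = 67, or 34 × 2 = 68.

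**1. The plan's own figure.** Cohen's h = 2·asin(√0.97) − 2·asin(√0.88) = 2.7934 − 2.4341 = 0.3593.

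n = ((1.645 + 1.282)/0.3593)² = 66.3, so 67. The formula's approximate power at 67 is 90.3%. The 67 is reproduced. The same formula at 80% power gives 48, so 67 was not derived from the synopsis's 80%.

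**2. Lower bounds at the critical counts**, with p = x/n and z = 1.645:
- Clopper-Pearson: 5% quantile of Beta(x, n−x+1)
- Wilson: [p + z²/2n − z√(p(1−p)/n + z²/4n²)] / (1 + z²/n)
- Jeffreys: 5% quantile of Beta(x+½, n−x+½)
- Arcsine: sin²(asin√p − z/(2√n))
- Wald: p − z√(p(1−p)/n)

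| Result | Clopper-Pearson | Wilson | Jeffreys | Arcsine | Wald |
|---|---|---|---|---|---|
| 64/67 | 0.8883 | 0.8931 | 0.8985 | 0.9048 | 0.9137 |
| 63/67 | 0.8686 | 0.8735 | 0.8784 | 0.8841 | 0.8927 |
| 64/68 | 0.8704 | 0.8753 | 0.8801 | 0.8858 | 0.8942 |

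Against 0.88, 64/67 passes with every method. 63/67 fails with the first three and passes with arcsine and Wald. 64/68 fails with the first two and passes with the other three.

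**3. Operating characteristics.** With independent insertions, the number of failures is binomial. Type I error is P(failures ≤ k) at failure rate 0.12; power is the same probability at 0.03.

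| n | Allowed failures k | Type I error | Power |
|---|---|---|---|
| 67 | 3 | 3.29% | 85.8% |
| 67 | 4 | 8.35% | 94.9% |
| 68 | 3 | 3.02% | 85.3% |
| 68 | 4 | 7.74% | 94.6% |

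No k at either size gives both at most 5% and at least 90%. The chance of exactly 4 failures in 67 at the assumed 97% rate is 0.949 − 0.858, or about 9%.

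**4. Larger final samples, Clopper-Pearson rule.**

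| n | k | Type I error | Power |
|---|---|---|---|
| 73 | 3 | 1.9% | 82.4% |
| 74 | 4 | 4.9% | 92.8% |
| 81 | 4 | 2.8% | 90.3% |
| 84 | 4 | 2.1% | 89.2% |
| 85 | 5 | 4.9% | 95.7% |

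Both targets are met at n = 74 to 81, and again from 85 upward (checked to 199), but not at 67 to 73 or 82 to 84. Wilson agrees with Clopper-Pearson at 67 and 68, but allows one more failure and exceeds 5% at n = 71 to 73 (6.2%, 5.7%, 5.3%) and at 83 to 84 (5.7%, 5.3%).

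**5. Correlation within patients.** The documents give none, so a range is assumed. Take 34 patients with 2 insertions each, P(both fail) = q² + ICC·q(1−q) for failure rate q, and at most 3 failures in all.

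| Assumed ICC | Type I error | Power |
|---|---|---|
| 0 | 3.0% | 85.3% |
| 0.2 | 4.3% | 83.5% |
| 0.3 | 5.0% | 82.8% |
| 0.5 | 6.5% | 81.3% |

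**The case against.** The sample-size arithmetic contains no slip. SAP 3.2.1 says the number is approximate, names its approximation, and under it power is 90.3%. That stands: the fault is that the approximation does not carry over to the rule actually used.

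The SAP is to be signed before database lock and already fixes the threshold, side, level and population, and nothing in it says the interval will be picked late. That is fair, but a signed text that is silent on the method does not rule out a late choice. The arcsine method a reader might infer from 3.2.1 is one that exceeds 5% at this size.

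The method might be named in something not supplied, such as the tables section that SAP 8.2 refers to, or the full protocol revision on which the SAP rests. This cannot be excluded. The supplied text of 5.2 and 6.1.1, where the method belongs, does not name it.

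Wilson would give the same cut-off at 67 and 68, so insisting on Clopper-Pearson could look like a preference. It would be one if n were fixed. Because 67 is a minimum and Wilson exceeds 5% at some nearby sizes, the exact bound is the safer choice.

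Finally, the exact bound holds 5% only if insertions are independent; the range above shows it slightly exceeded at an ICC of 0.3. That stands as a limit on the fix, and the replacement text should say so.

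**Conclusion.** The concern holds and should be fixed before database lock. At the planned minimum, the rule in SAP 6.1.1 has either 3.3% type I error with 85.8% power, or 8.35% with 94.9%, depending on an interval the SAP does not name. The 90% and 5% in SAP 3.2.1 are not achieved together at 67 or 68 insertions.

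The power loss on the valid branch is about 4 points, remains above the synopsis's 80%, and would not by itself call for action. What does is that one plausible result, 4 failures, is a success or a failure according to an unspecified choice. These figures are exact binomial results for independent insertions and a true rate of 97%. Positive correlation within patients would generally worsen both error and power.

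**What to change.** 1. **SAP 6.1.1:** name the exact (Clopper-Pearson) one-sided 95% lower bound, applied to the number of insertions actually analysed. State what this means: at most 3 failures at 67 or 68 insertions (and up to 73), at most 4 at 74 to 84.
2. **SAP 3.2.1:** keep 67 and replace the 90% power claim with text such as: *At 67 insertions, assuming independent insertions, this rule has about 86% power at a true success rate of 97% and a type I error of about 3.3%. This meets the 80% power planned in the protocol synopsis. Positive within-patient correlation would generally worsen both figures.*
3. **In the same edit:** reconcile the 80% in the synopsis with the 90% in the SAP, so that one planned power is stated.

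The cost is two SAP edits before lock and no change in enrolment. The sponsor states a lower power (about 86%) and gives up counting 63/67 as non-inferior. If the sponsor prefers to keep 90% power with 5% error, the smallest sample that meets both under the exact rule is 74 insertions, which at 2 per patient is 37 patients, 3 more than planned.
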